#### 7.6.5 Electrocardiograms

The following quantitative ECG measurements will be taken during the study:

- heart rate (bpm);
- PR interval (msec);
- QRS interval (msec);
- Fridericia corrected QT (QTcF) interval (msec)

Descriptive summaries and changes from baseline will be presented by treatment group for the quantitative ECG measurements listed above and the qualitative overall ECG interpretation (categorized as normal; abnormal, insignificant; and abnormal, significant).

Shift tables will present changes from baseline in ECG interpretation (categorized as normal; abnormal, not clinically significant; and abnormal, clinically significant) to each post-baseline visit.

[REDACTED]

[REDACTED]

[REDACTED]

[REDACTED]

[REDACTED]

[REDACTED]

## 7.7 ANALYSIS OF SERUM CONCENTRATIONS OF BIO89-100

The serum concentration of BIO89-100 over time will be listed and plotted by individual and also summarized by treatment group. Serum concentration data will also be presented using arithmetic statistics.

## 7.8 PHARMACOKINETICS ENDPOINTS

For summarization of PK concentration values and data analysis, assessments that are below the lower limit of quantification (LLOQ) will be set to zero prior to summarization. For PK concentration graphs, assessments that are below the lower limit of quantification will be set to half of LLOQ prior to graphing. For PK concentration assessments that are above the upper limit of quantification (ULOQ), the record will be set to missing prior to summarization or graphing.

Individual and mean BIO89-100 serum concentrations for each nominal timepoints will be listed, summarized and plotted versus time. PK parameters will be listed for each subject in the analysis set and summary descriptive statistics will be presented.

If data are suitable, PK parameters include:

- Maximal observed serum concentrations ( $C_{max}$ ) within a dosing interval
- Area under the serum drug concentration by time curve within a dosing interval ( $AUC_{0-\tau}$ )
- Time to achieve  $C_{max}$  ( $T_{max}$ )
- Terminal elimination half-life ( $t_{1/2}$ )
- Trough concentration

Additional PK parameters may be calculated if also deemed appropriate.

[REDACTED]

[REDACTED]

Protocol No: BIO89-100-221 V3.0  
Version: 1.0

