## 4.2 SECONDARY EFFICACY ENDPOINTS

- The proportion of subjects who achieve TG < 500 mg/dL at Week 8
- Percentage change in VLDL-C, LDL-C, non-HDL-C, HDL-C, VLDL-TG, ApoB, remnant lipoprotein cholesterol (RLP-C), hsCRP from baseline to Week 8
- Percentage change in fasting plasma glucose, adiponectin, and body weight from baseline to Week 8
- The serum BIO89-100 concentrations and PK parameters
- Percentage change and change from baseline in hepatic steatosis using Magnetic Resonance Imaging – Whole Liver Proton Density Fat Fraction (MRI-PDFF)

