#### 4.5 PHARMACOKINETICS ENDPOINTS

PK parameters will be calculated by non-compartmental methods from the BIO89-100 serum concentration data in Intensive PK subgroup, if the data are suitable.

- Maximal observed serum concentrations ( $C_{max}$ ) within a dosing interval
- Area under the serum drug concentration by time curve within a dosing interval ( $AUC_{0-\tau}$ )
- Time to achieve  $C_{max}$  ( $T_{max}$ )
- Terminal elimination half-life ( $t_{1/2}$ )
- Trough concentration

Additional PK parameters may be calculated if also deemed appropriate.

PK parameters will be calculated separately by designee of 89BIO.

Serum concentration and PK parameters data will be analyzed using the Pharmacokinetics Analysis Set.

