### Other Study-Specific Laboratory Assessments:

- BIO89-100 level (to be evaluated by bioanalytical laboratory)
- TSH level
- Serum hCG pregnancy test, Urine hCG pregnancy test, FSH level

- Urine drug screen including amphetamines, barbiturates, cocaine metabolites, opiates, benzodiazepines, cannabinoids and phencyclidine
- Virology - Human Immunodeficiency Virus (HIV) antibody, hepatitis B surface antigen (HBsAg, and HCV antibody). To determine current infection status, if HBsAg positive Hepatitis B Virus (HBV) DNA will be measured or if HCV antibody positive, HCV Ribonucleic Acid (RNA) will be measured.
- 24-hour urine for cortisol, [REDACTED], [REDACTED], [REDACTED], total Insulin, hsCRP, [REDACTED], [REDACTED], Serum adiponectin, and [REDACTED]  
[REDACTED].

For all other assessments that are below the lower limit of quantification will be imputed to half of the LLOQ for summarization; assessments that are above the upper limit of quantification will be imputed to the ULOQ for summarization. For listings, records that are LLOQ or ULOQ will be listed as such together with the imputed value in separate columns.

Laboratory results will be presented as received from the central laboratory (or kit provided by the central lab).

Descriptive summaries by treatment groups will be produced for the laboratory tests.

Shifts (low/normal/high) from the relevant baseline tables based on the normal ranges will be constructed. The shifts will be performed from the baseline to each post-baseline visit, and to minimum and maximum post-baseline visit.

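### SAP 7.8 sets PK concentrations above the ULOQ to missing, which lowers mean concentrations whenever such values occur; the SAP's own ULOQ substitution in 7.6.2 is less biased

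*SAP*

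**What the plan says.** SAP 7.8 treats the two ends of the assay range differently. For summaries, "assessments that are below the lower limit of quantification (LLOQ) will be set to zero prior to summarization"; for graphs, the same low values become half the LLOQ. Either way they stay in. For a concentration above the ULOQ, "the record will be set to missing prior to summarization or graphing".

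The summaries that this reaches are set out in the same section ("Individual and mean BIO89-100 serum concentrations for each nominal timepoints will be listed, summarized and plotted versus time") and in SAP 7.7, which adds summaries by treatment group: "Serum concentration data will also be presented using arithmetic statistics".

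SAP 7.6.2 has the opposite rule for laboratory results: "assessments that are above the upper limit of quantification will be imputed to the ULOQ for summarization". That sentence limits itself to all other assessments, but the list just above it includes "BIO89-100 level (to be evaluated by bioanalytical laboratory".

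On the derived parameters, SAP 4.5 says "PK parameters will be calculated separately by designee of 89BIO". SAP 4.2 names "The serum BIO89-100 concentrations and PK parameters" among the secondary endpoints. No ULOQ value, expected share above it, PK variability or re-assay rule is visible in either document. Part of SAP 7.8 after the parameter list is blacked out.

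**The concern.** A concentration above the ULOQ is censored, not unknown: the laboratory has established that it exceeds the limit. Setting it to missing handles it as if the sample had never been taken, and the chance of being dropped depends on the value itself. Low values are kept, so the summary loses only its upper end.

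What is at stake is the description of exposure. Mean concentration by arm and time point would be too low where concentrations are highest, and so the contrast in exposure between arms would look smaller than it is. Protocol 4.2 says the study's results are meant to inform Phase 3 dose selection. The peaks come from an optional intensive-sampling subset of at most 45 subjects (SAP 3.2), so a few dropped values could move an arm's mean. The two SAP sections also leave a programmer unsure which rule governs the BIO89-100 level.

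**Working it through.** The plan gives no figure to reproduce, so the check has two parts: the direction, which needs no distributional assumption, and an illustrative size, which rests on assumptions.

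**Direction.** Let C be a concentration, U the ULOQ and f = P(C > U).

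- Set to missing: the summary estimates E[C | C ≤ U].
- Set to the ULOQ: it estimates (1 − f)·E[C | C ≤ U] + f·U.
- True mean: (1 − f)·E[C | C ≤ U] + f·E[C | C > U].

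Because E[C | C ≤ U] ≤ U < E[C | C > U], the three are ordered: missing ≤ ULOQ substitution < truth whenever f > 0. Both rules are biased downward, and substitution is never worse. If f = 0, neither has any effect.

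**Size (assumed lognormal).** With σ² = ln(1 + CV²) and z the standard normal quantile at 1 − f:

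- missing: bias = Φ(z − σ)/(1 − f) − 1
- ULOQ: bias = Φ(z − σ) + f·exp(zσ − σ²/2) − 1

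Worked case, CV 50% and f = 10%: σ² = ln 1.25 = 0.223, σ = 0.472, z = 1.282, Φ(0.809) = 0.791.

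- missing: 0.791/0.9 − 1 = −12.1%
- ULOQ: 0.791 + 0.1 × 1.639 − 1 = −4.5%

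Other settings (missing / set to ULOQ):

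| Share above ULOQ | CV 30% | CV 50% | CV 80% |
|---|---|---|---|
| 5% | −4.0% / −1.1% | −7.4% / −2.3% | −13.0% / −4.9% |
| 10% | −6.8% / −2.2% | −12.1% / −4.5% | −20.2% / −8.9% |
| 20% | −11.5% / −4.7% | −19.5% / −9.0% | −30.6% / −16.3% |

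The shares and the CVs are both assumptions; neither is in the documents.

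**Gradient across concentrations.** Take one common ULOQ, CV 50%, and geometric means proportional to the single dose, as might hold at a time point where every arm has just had active drug. Place the ULOQ so that 10% of 36 mg values exceed it. Each lower dose then has z larger by ln(36/dose)/σ. For 27 mg, z = 1.282 + 0.288/0.472 = 1.891, which puts 2.9% above the ULOQ.

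| Dose | Missing | Set to ULOQ |
|---|---|---|
| 36 mg | −12.1% | −4.5% |
| 27 mg | −5.0% | −1.4% |
| 18 mg | −0.8% | −0.2% |
| 9 mg | 0.0% | 0.0% |

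The bias follows concentration at the time point, not nominal dose as such.

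**Cmax, only if blanked records reach the derivation.** A simulated one-compartment subcutaneous profile was used, with an assumed absorption half-life of 15 h, elimination half-life of 70 h and 6 samples. With 10% of 36 mg subjects peaking above the ULOQ, mean Cmax changes by −4.0%, −6.9% and −12.1% at CV 30%, 50% and 80%. With 20% of them it changes by −7.9%, −13.0% and −21.1%.

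**The case against.** The strongest reply is that the rule may never operate. The documents give no ULOQ, every subject's trough sample is taken shortly before dosing or at the end-of-treatment visit (Protocol 8.5), and troughs are the samples least likely to exceed an upper limit. This stands: the size is unknown and may be zero.

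A reader might infer that Cmax is biased too. The documents do not establish that. The ULOQ sentence is confined to summaries and graphs, whereas the LLOQ sentence in the same section also covers data analysis, and the parameters are derived separately. Cmax, and with it AUC and Tmax, is affected only if that derivation uses the blanked records. What remains is that the visible text gives no ULOQ rule for that step.

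A reader might also infer that exposure at the highest doses is understated. That is looser than the text allows: 36 mg every two weeks averages 18 mg a week, and a trough two weeks after a dose need not be the highest.

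Nor can one conclude that no re-assay is planned. The bioanalytical laboratory's method is not among these documents, and part of SAP 7.8 is blacked out.

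It is also fair that SAP 7.6.2 can be read as leaving PK concentrations to 7.8, that ULOQ substitution is itself biased, and that PK is a secondary endpoint with no visible hypothesis test. SAP 7.1 offers some visibility, because summaries show the number of subjects and listings show non-imputed data. But a smaller number of subjects does not tell an over-range sample from one never taken.

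**Conclusion.** The concern holds in conditional form. If any reported concentration exceeds the ULOQ, SAP 7.8 biases mean concentrations by arm and time point downward, most in the arms and time points with the highest concentrations. The direction is certain. The size is not: about −12% against −4.5% under the 10%, CV 50% illustration, and zero if no value is above the limit.

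This is a stated rule with a known direction of bias, not a missing detail, and the SAP already contains a less biased one. An effect on Cmax, AUC or Tmax is possible but not shown. The consequence is confined to the PK description; the primary triglyceride analysis is unaffected. It is a minor point, worth making because the correction is cheap.

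**What to change.** In SAP 7.8, replace the rule for values above the ULOQ with the following:

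1. Where the laboratory provides a quantified re-assay result, use it.
2. Otherwise set the value to the ULOQ for summaries and graphs, as SAP 7.6.2 does, and flag it.
3. Report the number of values above the ULOQ per arm and time point.
4. State that the same handling applies to the derivation of the PK parameters.
5. Reconcile 7.6.2 with 7.8 by saying which section governs the BIO89-100 level that 7.6.2 lists.

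The cost is a few sentences in the SAP, a flag and a count column. The drawback is that ULOQ substitution still leaves a downward bias, smaller than under the present rule; the flags and counts let a reader judge how much it matters.

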## Statistical Analysis Plan

Term	Percentage
GMOs	95
Organic	90
Natural	85
Artificial	75
Organic	70
Natural	65
Artificial	60
Organic	55
Natural	50
Artificial	45
Organic	40
Natural	35
Artificial	30

---

## 8 LIST OF PLANNED TABLES, FIGURES

The list of table, listing, and figure mockups are included in TLF Shell, as a separate document.

## 9 APPENDICES

### Appendix 1 Schedule of Activities (SOA)

Study Period (Duration)	Screening/ Lifestyle Stabilization (Min 4 weeks to Max 6 weeks)	Screening/ TG Qualification (2 Week)	Screening/ TG Sample	Double-blind Treatment (8 Weeks)								Follow-up (4 Weeks)
Visits												
Study Day b												
Informed consent	X											
Inclusion/exclusion	X	X	X	X								
Randomization				X								
Demography, medical history	X											
Physical examination	X	X c	X c	X c	X c	X c	X c	X c	X c	X c	X	X
Body weight	X	X	X	X				X			X	X
Height d	X											
BMI (derived)	X										X	
Vital signs (BP e , heart rate e , RR) and body temperature	X	X		X				X			X	X

Study Period (Duration)	Screening/ Lifestyle Stabilization (Min 4 weeks to Max 6 weeks)	Screening/ TG Qualification (2 Week)	Screening/ TG Sample	Double-blind Treatment (8 Weeks)								Follow-up (4 Weeks)
Visits												
Study Day b												
Hematology, blood chemistry and coagulation panel	x f		x f	x f				x f			x f	x f
Urinalysis	x			x			x			x	x	x
Thyroid panel (TSH, free T4, and free T3)	x		x							x	x	
12-lead ECG	x			x			x			x	*	
History of drug and/or alcohol abuse, urine drug test, and alcohol consumption test	x g		x g,h	x h			x h	x h		x h	x h	x h
Serum lipids, lipoproteins and apolipoproteins (TG, [REDACTED], VLDL-C, VLDL-TG, LDL-C, HDL-C, non-HDL-C, RLP-C, [REDACTED] ApoB, [REDACTED], [REDACTED])		x	x i	x			x	x i		x i	x	x

Study Period (Duration)	Screening/ Lifestyle Stabilization (Min 4 weeks to Max 6 weeks)	Screening/ TG Qualification (2 Week)	Screening/ TG Sample	Double-blind Treatment (8 Weeks)								Follow-up (4 Weeks)	
Visits													
Study Day b													
Inflammatory biomarker (hsCRP)				X				X				X	
	■ and serum adiponectin, total												
Intensive PK (optional) k				X	X	X	X	X	X	X	X		
Trough PK (for all subjects) k				X	X	X		X				X	
HIV, HCV and HBV Serology l		X											
FSH if required to determine menopausal status		X											
Serum pregnancy test (WOCBP)		X										X	
Urine pregnancy test (WOCBP)			X	X				X				X	

Study Period (Duration)	Screening/ Lifestyle Stabilization (Min 4 weeks to Max 6 weeks)	Screening/ TG Qualification (2 Week)	Screening/ TG Sample	Double-blind Treatment (8 Weeks)								Follow-up (4 Weeks)	
Visits													
Study Day b													
Jug dispensed for 24-hour urine collection for cortisol and creatinine m			X							X			
Archived serum and plasma samples n				X				X			X		
Investigational product dosing p				X	X	X	X	X	X	X			
AE and SAEs including hypersensitivity-related AEs q	X	X		X			X				X	X	
Concomitant medication	X	X		X			X				X	X	
Review of lifestyle and alcohol use r	X	X	X	X			X	X		X	X	X	
MRI-PDFF s				X							X		
FGF21				X									

Shaded columns indicate visits that can be conducted by home health providers.

Abbreviations: AE = adverse event; [REDACTED]; ALT = alanine aminotransferase; ALP = alkaline phosphatase; [REDACTED]; ApoB = apolipoprotein B100; [REDACTED] aPTT = activated partial thromboplastin time; AST = aspartate aminotransferase; [REDACTED] [REDACTED] BP = blood pressure; BMI = body mass index; BUN = Blood urea nitrogen; CK = creatine kinase; CKD-EPI = chronic kidney disease epidemiology collaboration; [REDACTED]; DNA = deoxyribonucleic acid; ECG = electrocardiogram; eGFR = estimated glomerular filtration rate; EOS = end of study; EOT = end of treatment; [REDACTED]; FGF21 = fibroblast growth factor 21; FSH = follicle-stimulating hormone; GGT =

gamma-glutamyl transferase; [REDACTED]; HBsAg = Hepatitis B surface antigen; HCV = Hepatitis C Virus; HDL-C = high-density lipoprotein-cholesterol; HHP = home health provider; HIV = Human Immunodeficiency Virus; hsCRP = high-sensitivity C-reactive protein; [REDACTED]  
■ INR = international normalized ratio; LDL-C = low-density lipoprotein-cholesterol; [REDACTED] non-HDL-C = non-high-density lipoprotein-cholesterol; MCV = mean corpuscular volume; MCH = mean corpuscular hemoglobin; MCHC = mean corpuscular hemoglobin concentration; MRI = Magnetic resonance imaging; MRI-PDFF = Magnetic Resonance Imaging – Whole Liver Proton Density Fat Fraction; [REDACTED];  
PK = pharmacokinetics; PT = prothrombin time; RNA = ribonucleic acid; RR = respiratory rate; RLP-C = remnant lipoprotein-cholesterol; SAE = serious adverse event; SoA = Schedule of Assessments; T3 = triiodothyronine; T4 = thyroxine; [REDACTED]; TG = triglyceride; TSH = thyroid-stimulating hormone; V = Visit; VLDL-C = very low-density lipoprotein cholesterol; VLDL-TG = very low-density lipoprotein triglycerides; WBC = white blood cell; WOCBP = women of childbearing potential.

Body posture during TG, BP, heart rate, RR and body temperature measurement needs to be the same (e.g., sitting, semi-erect, or supine) throughout the study with resting for at least 5 min prior to measurement at each study visit.

Fasting blood samples should be taken after at least 12 hours of fasting. (It is recommended that subjects fast no more than 14 hours.) Fasting includes food and all beverages except for non-mineral water.

Hematology: Hemoglobin, hematocrit, RBC count, reticulocyte count, MCV, MCH, MCHC, platelet count, WBC count, total neutrophils, eosinophils, monocytes, basophils, lymphocytes.

Blood chemistry: BUN, creatinine (eGFR using CKD-EPI equation), fasting plasma glucose, calcium, sodium, potassium, chloride, total CO2 (bicarbonate), AST (SGOT), ALT (SGPT), ALP, GGT, total bilirubin, direct (conjugated) bilirubin, indirect (unconjugated) bilirubin, CK, uric acid, albumin, total protein. Coagulation panel: INR, aPTT, PT.

Urinalysis: pH, glucose, protein, blood, ketones, nitrites, leukocyte esterase, urobilinogen, urine bilirubin, microscopy.

a = If [REDACTED] is required, only assessment at that visit is TG measurement.

b = [REDACTED]

c = Symptom-driven physical assessment for applicable reported AEs. Can be conducted on site during a scheduled or unscheduled visit or by a home health provider (HHP) if identified on the delegation log. d = Height at screening [REDACTED] only.

e = Starting from randomization, pre-dose BP and pulse will be measured in duplicate. The first measurement will be initiated before dosing with sitting/semi-erect or supine position and resting for at least 5 minutes prior to measurements. BP and pulse are to be repeated at least 1 minute apart. Additional vital signs measurements may be done if clinically indicated.

f = Coagulation panel will be done at [REDACTED] only.

g = History of drug and/or alcohol abuse taken at screening [REDACTED] only. Urine drug test will be performed at [REDACTED] only. h= Alcohol breathalyzers will be used. Results >0.01% will be considered as positive.

i = [REDACTED]

j = [REDACTED]

[REDACTED]  
[REDACTED]  
[REDACTED]  
[REDACTED]  
[REDACTED]  
[REDACTED]

iii. [REDACTED]  
[REDACTED]

k = Subjects will be included in either the Intensive PK scheme (optional) or Trough PK scheme (all subjects). [Table 5 in the protocol](#) details sampling times for the Intensive PK scheme. Intensive PK subjects will have additional visits on [REDACTED]. For the Trough PK scheme, blood samples will be taken within 4 hours prior to dosing on specified dosing days or during EOT visit [REDACTED] for all subjects.

Note: Where the Intensive PK schedule overlaps with the Trough PK schedule, only 1 PK measurement should be taken at those time points.

l = Serology tests will include HBsAg, HCV, and HIV 1 and 2 antibodies. HBV and HCV determined by antibodies first and, if positive, by DNA/RNA.

m = Ambulatory 24-hour urine collection for analysis of cortisol and creatinine to be initiated the day prior to [REDACTED]. Subject will start collection 24 hours before coming into the clinic and bring the sample to the visit. The 24-hour urine collection jug is dispensed at [REDACTED] so collection can be completed and brought to [REDACTED], respectively. The jug may be provided at the site or by an HHP.

n = Archived for possible analysis of additional biomarkers. This is optional and by subject consent.

o = [REDACTED]  
[REDACTED]  
[REDACTED]

[figure not shown]
p = Subjects randomized to BIO89-100 36 mg Q2W group will receive BIO89-100 at [REDACTED] and placebo at [REDACTED] to maintain the blind. Home health IP administration may occur on [REDACTED].

q = When IP is scheduled to be administered by an HHP, a subject's spontaneous reports of AE/SAE will be reported to the site staff who will follow-up and evaluate the need for an unscheduled visit for AE assessment. The sites/HHP may take non-personally identifying photographs of potential injection site reactions (optional).

r = Study coordinators should reinforce maintenance of eating and exercise habits without weight loss or gain of 5% for the duration of the study, and alcohol consumption restrictions 48 hours prior to fasting blood work.

s = After a consenting subject's [REDACTED], the site should preemptively schedule the baseline MRI-PDFF to occur within the following projected visit windows to ensure an MRI appointment is available to be performed after the [REDACTED] TG result  $\geq 350$  mg/dL is known. For the main cohort, MRI-PDFF is optional and should occur prior to [REDACTED]. For the fibrate expansion cohort, MRI-PDFF of  $\geq 6.0\%$  is required for enrollment and should be performed between [REDACTED] [REDACTED]. The follow-up MRI at [REDACTED] should only be performed if the baseline liver MRI-PDFF value is  $\geq 6.0\%$ . MRI-PDFF is mandatory in the fibrate expansion cohort.

## Appendix 2 SAS Sample Code

The image shows a large block of SAS sample code that has been heavily redacted. The code is organized into several sections, each starting with a line of text followed by a series of horizontal bars of varying lengths. The redaction bars are black and completely obscure the original text of the code. The sections are separated by blank lines and some vertical lines of text.
